22.3. Arm Objective

The purpose of the Motivational Interviewing Arm is to increase motivation and preparation to for smoking cessation treatment among individuals who express an interest in quitting smoking but are not currently ready to enter smoking cessation treatment, and are otherwise eligible for participation in the current protocol 12-DA-N474 or protocol 13-DA-N485. If, after a prescribed period of motivational interviewing, the participant and the study therapist feel that the participant is ready to enter treatment for smoking cessation, they will be offered admission into either protocol 12-DA-N474 or protocol 13-DA-N485.

22.4 Number and type of subjects

This study arm will recruit 300 current smokers who meet criteria for participation in protocol 12-DA-N474 (see section 3 Subjects) or protocol 13-DA-N485) but who are not currently ready to enter treatment for smoking cessation.

Principal Investigator: [name].

APPROVED STUDY POPULATION						
	FEMALE	MALE	TOTAL	FEMALE	MALE	TOTAL
	ENROLLMENT	ENROLLMENT	ENROLLMENT	COMPLETERS	COMPLETERS	COMPLETERS
APPROVED	150	150	300	150	150	300

Date: March 2, 2022

OLILINO						
NIH TARGETED/PLANNED ENROLLMENT						
		Sex/Gender				
	ETHNIC CATEGORY					
		Females	Males	Total		
Hispanic or Lati	ino	6	6	12**		
Not Hispanic or Latino		144	144	288		
Ethnic Category: Total of All Subjects*				300*		
	RACIAL CATEGORIES					
American Indian/Alaska Native		1	1	2		
Asian		3	3	6		
Native Hawaiian or Other Pacific Islander		0	0	0		
Black or Africar	n American	99	99	198		
White		47	47	94		
Racial Categories: Total of All Subjects*		150	150	300*		

^{*}The "Ethnic Category: Total of All Subjects" must be equal to the "Racial Categories: total of All Subjects."

23.5. Arm design and procedures

An initial session will be conducted to assess individual motivation/preparation to quit. During this session participants will complete the treatment preparation and motivation to quit measures outlined in Appendix 9 and meet briefly with a study therapist (~60min). This initial session will be followed by 1 to 10 sessions of motivational interviewing with a study therapist (each session ~20-60min). Motivational interviewing techniques are based on the SAMHSA Treatment Improvement Protocol (TIP) for enhancing motivation for substance abuse treatment (Center for Substance Abuse Treatment, 1999). Individuals recruited for this study will vary in their motivation and preparation to quit. Consequently, the number of motivational interviewing sessions will vary according to individual need as determined by the study therapist, with a maximum of 10 sessions per individual.

23.6 Storage of data

Clinical data will be stored in the Clinical Data Warehouse (CDW) and in clinical research charts. Research charts will be stored in locked filing cabinet, in a locked room at the NIDA-IRP. One copy of the consent form is kept in the participant's NIDA-IRP medical chart, the other is kept in a limited access, locked cabinet with other consent forms from the same protocol. Participant data contained within files on the NRB data drive are identified by ARC number, and not by other personal identifiers such as name.

23.7 Risks/discomforts

Questionnaire and Characterization Measures

The questions asked may be perceived as embarrassing or may cause anxiety or distress. Nevertheless, such reactions are expected to be temporary and to rapidly dissipate spontaneously.

Risk Minimization. Participants will be advised prior to completing these measures that they may refuse to answer any questions that cause them discomfort. Furthermore, any participant who experiences anxiety or distress as a result of these assessments will be able to speak to a NIDA-IRP mental health professional to discuss this.

Date: March 2, 2022 Principal Investigator: [name].

23.8 Outcome measures/Statistical Analysis

There will be no outcome measures or collation and analysis of data at a group-level in this arm of the study.

23.9. Human subjects protection

The same as outlined for above in Section 12. Human Subjects Protection

23.10. Anticipated benefit

Direct benefits: motivational interviewing should help increase participant's motivation to participate in smoking cessation treatment, which should in turn decrease their smoking behavior and withdrawal discomfort.

23.11 Consent documents/process, Data and safety Monitoring, Quality Assurance, Adverse event and unanticipated problem reporting, Alternatives to participation, Confidentiality, Conflict of Interest

Details for the above sections are identical to those outlined within Sections 14-19 of the main protocol document.

23.12 Research and Travel Compensation

Participants will be reimbursed \$20 per hour for the initial assessment visit but will not receive payment for the motivational interviewing visits. They will also receive \$15 travel compensation for each visit. Based on motivational counseling visits and a single pre-assessment visit, anticipated maximum compensation for participation in the Motivational Interviewing Arm of this study is \$185.

Principal Investigator: [name].

Date: March 2, 2022

23. Transcranial Direct Current Stimulation (tDCS) Arm

24.1. Arm Title

474 - Transcranial Direct Current Stimulation (tDCS) to reduce effects of the Nicotine Withdrawal Syndrome

24.2. Arm Background

Cigarette smoking remains the leading cause of preventable death and disease in the United States, accounting for 480,000 deaths each year (CDC 2016). Despite our deeper understanding of the neurobiology of nicotine addiction and drug abuse over the past 10 years (Nestler 2005, Everitt and Robbins 2005, Koob and Volkow 2010, Goldstein and Volkow 2011), current pharmacological interventions for smoking cessation are highly inadequate, with the most efficacious treatment (varenicline) having only about 27% absolute cessation rate according to recent meta-analysis (Cahill 2013, 2014). Additionally, symptoms of nicotine withdrawal remain a major impediment for smokers trying to quit, with most quit attempts failing within the first week of abstinence when withdrawal symptoms are at their height (Hughes 1992, Sutherland et al 2017).

Recent findings based on resting state functional connectivity (rsFC) revealed that the brain can be divided into multiple large-scale functional networks, many of which have been found to contribute to psychiatric disease (Lu and Stein 2014, Turk-Browne 2013, Yeo et al 2011, Fox et al 2014). Addiction has been hypothesized as an imbalance within and between three of these networks (Lerman et al 2014, Pariyadath et al 2015, Fedota and Stein 2015, Sutherland et al 2012). Specifically, the cognitive and affective disturbances of nicotine withdrawal syndrome have been attributed to a reduced within-network connectivity of the Executive Control Network (ECN) and increased within-network connectivity of the Default Mode Network (Sutherland et al 2017). Additionally, the Salience Network (SN) has been called the "gatekeeper" for these two networks, and its function may be dysregulated in addictive disorders, as well (Sutherland et al 2017).

A treatment that acts by modifying these large-scale brain networks with specificity may help address the underlying pathophysiology of nicotine addiction and improve clinical outcomes (Dunlop et al 2016). Transcranial Direct Current Stimulation (tDCS), a type of Non-invasive Brain Stimulation (NIBS), has the potential to modify neuronal circuits by application of a subthreshold conductive current through the scalp. Two potential targets for tDCS as a smoking cessation aid are the dorsolateral pre-frontal cortex (dlPFC), a node of the ECN, and the ventromedial prefrontal cortex (vmPFC), a node of the DMN (Lerman et al 2014). tDCS can potentially strengthen the control of the ECN through excitatory stimulation of the dlPFC, and weaken the influence of the DMN by inhibitory stimulation of the vmPFC.

24.3. Arm Objective

The goal of the Transcranial Direct Current Stimulation (tDCS) Arm is to investigate the effects of tDCS on modulating large-scale brain networks dysregulated in nicotine addiction and withdrawal. Non-smokers and matched smokers (in both nicotine deprived and sated conditions) will be recruited for a randomized, sham-controlled, double-blind, repeated measures tDCS crossover study. tDCS will be used to probe the ECN and DMN by targeting the dlPFC with anodal (excitatory) stimulation, and the vmPFC with cathodal (inhibitory) stimulation (Pariyadath et al 2015). The effects of tDCS on brain activation patterns and cognitive control will be measured "online" while the subject is being scanned via MRI, allowing greater insight into the neurophysiological effects of tDCS.

Principal Investigator: [name].

Date: March 2, 2022

Arm Hypothesis: The nicotine withdrawal syndrome is a **3-network dysregulation** characterized by reduced network connectivity (1) within the ECN and (2) between the ECN and the SN, as well as increased network connectivity (1) within the DMN, and (2) between the DMN and the SN. These deficits can be remediated by application of tDCS to cortical nodes of the ECN and DMN networks. (**Figure 1a**).

[figure not shown]

Figure 1a: Hypothesis. Three network dysregulation in nicotine addiction and hypothesized effects of tDCS. The ECN and DMN are anticorrelated. In nicotine withdrawal syndrome, the within-network connectivity of the DMN is stronger than normal, and the within-network connectivity of the ECN is weaker than normal. This imbalance is mediated by dysregulated connectivity between the SN - DMN and the SN - ECN. $SN = Salience\ Network.\ ECN = Executive\ Control\ Network.\ DMN = Default\ Mode\ Network.\ dlPFC = dorsolateral\ prefrontral\ cortex.\ vmPFC = ventromedial\ prefrontal\ cortex.\ Image\ adapted\ from\ Lerman\ et\ al\ 2014.$

Alternative Hypothesis (1): Nicotine withdrawal syndrome is a 2-network dysregulation characterized by altered homeostatic regulation between the ECN and DMN. It is possible that the ECN normally acts to weaken the DMN, while the DMN normally acts to weaken the ECN. In the nicotine withdrawal syndrome, the ECN may have weakened control over the DMN, leading to a stronger within-network connectivity of the DMN and weaker within-network connectivity of the ECN. Anodal tDCS applied to the dlPFC can return the 2 networks to homeostatic regulation by strengthening the within-network connectivity of the ECN, while cathodal tDCS applied to the vmPFC can return the 2 networks to homeostatic regulation by weakening the within-network connectivity of the DMN. (Figure 1b).

[figure not shown]

Figure 1b: Alternative hypothesis. Two network dysregulation in nicotine addiction and hypothesized effects of tDCS. $SN = Salience \ Network. \ ECN = Executive \ Control \ Network. \ DMN = Default \ Mode \ Network. \ dlPFC = dorsolateral \ prefrontral \ cortex. \ vmPFC = ventromedial \ prefrontal \ cortex. \ Image \ adapted \ from \ Lerman \ et \ al \ 2014.$

Principal Investigator: [name].

Alternative Hypothesis (2): It is also possible that the imbalances seen in nicotine addiction and withdrawal are due to an abnormal connectivity of only one of the two networks (DMN or ECN), either internally within the network or in connection with the Salience Network. The within-network connectivity of the DMN, or its between-network connectivity with the SN, may be stronger independently of changes to the ECN. Alternatively, the within-network connectivity of the ECN, or its between-network connectivity with the SN, may be weaker independently of changes to the DMN. The exact relationship may differ across individuals. In either case, anodal-dlPFC + cathodal-vmPFC tDCS is expected to bring the within and between network connectivities of the DMN and the ECN closer to the healthy control state.

Date: March 2, 2022

Specific Aims

Aim 1: To determine the effect of excitatory tDCS stimulation of the dlPFC and inhibitory tDCS stimulation of the vmPFC on the within-network and between-network connectivity of the Executive Control Network (ECN), Default Mode Network (DMN), and Salience Network (SN).

To understand the effect of anodal stimulation of the dlPFC, and cathodal stimulation of the vmPFC, we will compare the following tDCS montages: (1) anodal left-dlPFC + cathodal right-vmPFC stimulation, with anode over the left dlPFC and cathode over the right-vmPFC; (2) cathodal left-dlPFC + anodal right-vmPFC stimulation, in which polarity is reversed between the two electrodes, and (3) sham stimulation.

Sub-Aim 1.1: To determine the effect of tDCS stimulation on the Executive Control Network (ECN) and cognitive control during nicotine withdrawal. Resting state connectivity, behavioral tasks and functional imaging will be used to measure the strength of the ECN and cognitive control mechanisms in response to excitatory tDCS stimulation of the left dlPFC, a cortical node of the ECN.

Hypothesis 1.1.1. Anodal-dlPFC tDCS will strengthen the within-network connectivity of the Executive Control Network compared to sham as measured by resting state functional connectivity in *abstinent smokers* > *sated smokers* > *healthy controls*. Cathodal-dlPFC tDCS will have the inverse effect on ECN rsFC.

Hypothesis 1.1.2. Anodal-dlPFC tDCS will improve reaction time and response accuracy on cognitive control tasks (Parametric Flanker, Amygdala Reactivity Task, and N- back) in *abstinent smokers* > *sated smokers* > *healthy controls*. The improved behavioral performance will be correlated with increased BOLD signal in nodes of the ECN. Cathodal-dlPFC tDCS will have the inverse effect on BOLD signal and behavior.

Sub-Aim 1.2: To determine the effect of tDCS stimulation on the Default Mode Network (DMN) during nicotine withdrawal. Resting state connectivity, behavioral tasks and functional imaging, magnetic resonance spectroscopy, and white matter integrity will be used to measure the strength of the DMN and cognitive control mechanisms in response to excitatory tDCS stimulation of the left dlPFC, a cortical node of the ECN, and inhibitory tDCS stimulation of the left vmPFC, a cortical node of the DMN.

Hypothesis 1.2.1. Cathodal-vmPFC tDCS will weaken the within-network connectivity of the Default Mode Network as measured by resting state functional connectivity in *abstinent smokers* > *sated smokers* > *healthy controls*. Anodal-vmPFC tDCS will have the inverse effect on DMN rsFC.

Hypothesis 1.2.2. Cathodal-vmPFC tDCS will improve reaction time and response accuracy on cognitive control tasks (Parametric Flanker, Amygdala Reactivity Task, and N-back) in abstinent smokers > sated

CNS IRB Protocol Template (rev. 16Jun11)

Principal Investigator: [name].

smokers > *healthy controls*. The improved behavioral performance will be correlated with greater BOLD deactivation in nodes of the DMN during these tasks. Anodal-vmPFC tDCS will have the inverse effect on BOLD signal.

Sub-Aim 1.3: To determine the effect of tDCS stimulation on the Salience Network (SN) and its connectivity with the ECN and the DMN.

Hypothesis 1.3.1. Anodal-dlPFC tDCS will strengthen the between-network connectivity of the Executive Control Network to the Salience Network compared to sham as measured by resting state functional connectivity in *abstinent smokers* > *sated smokers* > *healthy controls*. Cathodal-dlPFC tDCS will have the inverse effect on ECN-SN rsFC.

Hypothesis 1.3.2. Cathodal-vmPFC tDCS will weaken the between-network connectivity of the Default Mode Network to the Salience Network as measured by resting state functional connectivity in *abstinent smokers* > *sated smokers* > *healthy controls*. Anodal-vmPFC tDCS will have the inverse effect on DMN-SN rsFC.

Hypothesis 1.3.3. Anodal-dlPFC + Cathodal-vmPFC tDCS will improve BOLD reactivity in nodes of the Salience Network in tasks that are known to those nodes (e.g. the insula in the Parametric Flanker Task). Cathodal-dlPFC + Anodal-vmPFC will have the inverse effect on BOLD reactivity in the SN.

Aim 2: To compare the effects of tDCS stimulation parameters on behavior, resting state functional connectivity, and BOLD fMRI signal.

Sub-Aim 2.1: To compare the effect of tDCS stimulation on a working memory task given during stimulation (online) and after stimulation (offline).

Hypothesis 2.1.1: Active tDCS stimulation will provide greater benefit on accuracy and response time, and increase BOLD activation in the ECN to a greater degree, during the "online" working memory task than during the "offline" working memory task.

Alternative Hypothesis 2.1.1(a): Active tDCS stimulation will provide greater the same degree of benefit on accuracy and response time, and increase BOLD activation in the ECN to the same degree, during the "online" working memory task as during the "offline" working memory task.

Alternative Hypothesis 2.1.1(b): Active tDCS stimulation will provide less benefit on accuracy and response time, and increase BOLD activation in the ECN to a smaller degree, during the "online" working memory task than during the "offline" working memory task.

Principal Investigator: [name].

Date: March 2, 2022

Aim 3: To compare the effects of tDCS stimulation on nonsmokers vs. smokers, in both the nicotine sated and nicotine deprived states.

Hypothesis 3.1. Active tDCS will have the greatest effect on the group farthest from normal resting functional connectivity at pre-stimulation baseline, i.e. smokers in withdrawal. The non-smoker group will respond the least to active tDCS. Smokers using a nicotine patch will respond to tDCS more than non-smokers, but not as much as smokers in withdrawal. Thus, *tDCS will have the greatest impact on network connectivity and behavior in the smoker-nicotine withdrawal group*, as measured by outcomes listed in Aim 1.

Aim 4: To evaluate the effect of individual variability on current localization, behavioral outcomes, and brain activation patterns in response to active tDCS stimulation.

Hypothesis 4.1. Anatomical Variability. As each individual has variation in head and brain size, skull thickness, and brain morphometry, it is expected that a standard tDCS application across all individuals will produce varied effects in each individual participant. Computer modeling of each participant's brain can approximate how standard tDCS stimulation parameters will affect each individual based on their own anatomy. We will use a post-hoc regression analysis to determine how outcome measures correlate with inter-individual anatomical variability.

Individuals who are predicted to have greater current flow through the dlPFC and vmPFC by computer modeling will also have greater responsivity to tDCS stimulation, as measured by outcomes listed in Aim 1.

Hypothesis 4.2. Psychological Variability. Cigarette smoking behavior is usually accompanied by a variety of co-morbid conditions and traits, such as depressed mood, increased anxiety, and use of substances such as marijuana and alcohol. Although participants will be excluded for serious co-morbidities, including moderate to severe mood or anxiety disorders, or substance use disorders (other than nicotine), the traits of these disorders fall on continuous scales that show variance among individuals before the diagnostic threshold. These individual differences can affect performance on the fMRI tasks, resting state functional connectivity, and response to tDCS.

We will use a post-hoc regression analysis to determine how these outcome measures correlate with interindividual differences in personality, mood, anxiety, and substance use. It is predicted that individuals prone to depressed mood, increased anxiety, and more frequent use of marijuana or alcohol will have more abnormal resting connectivity at baseline, and therefore will be more responsive to tDCS stimulation, as measured by outcomes listed in Aim 1.

Principal Investigator: [name].

Date: March 2, 2022

24.4. Number and type of subjects

There will be two study populations: 1) healthy nicotine-dependent adult participants who are current non-treatment seeking smokers; and 2) healthy non-smoking, non-drug dependent controls.

This study arm will recruit 60 current **non-treatment seeking smokers** (enrollees) with the expectation of 35 completers. Additionally, we will recruit 55 **non-smokers** (enrollees) attempted to match based on recruitment availability, by education, age, race, and gender, with the expectation of 45 completers (of either the Behavioral Pilot or tDCS Imaging study).

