Principal Investigator: [name].

Protocol 12-DA-N474: Identifying neurological mechanisms that underlie acute nicotine withdrawal and drive early relapse in smokers.

Approval Date: March 2, 2022

NCT 01511614

Date: March 2, 2022

Principal Investigator: [name].

Protocol Title: Identifying neurobiological mechanisms that underlie acute nicotine withdrawal and drive early relapse in smokers.

Abbreviated Title: Neurobiology of nicotine withdrawal

Protocol Number: 12-DA-N474

Date of This Submission/Version: March 2, 2022

Principal Investigator:

T Time par in vesti	B			
Name, Degree	Branch/Institute	Bldg/Rm	Phone/Fax	Email
[name]	NIDA/IRP//NRB	BRC/07A709 [name]	P: [contact] F: [contact]	[contact]

Total requested accrual:

Total Enrollees: 577 Completers: 500

Main Study:

120 Treatment-seeking smokers (enrollees), 85 Completers

42 non-treatment seeking smokers (enrollees), 35 completers.

Motivational Interviewing Arm:

300 people interested in quitting smoking, but not yet ready to set a quit date.

Transcranial Direct Current Stimulation (tDCS) arm:

60 non-treatment seeking smokers (enrollees), 35 completers

55 nonsmokers (enrollees), 45 completers. Up to the first 25 of these enrollees will complete the tDCS without MRI (Behavioral Pilot)

Project Uses Ionizing Radiation:	¥ No	☐ Yes
IND/IDE	₩ No	□Yes
Durable Power of Attorney	₩ No	☐ Yes
Multi-institutional Project	₩ No	☐ Yes
NIDA is the coordinating site		
Data and Safety Monitoring Board	¥ No	□ Yes

Date: March 2, 2022

Principal Investigator: [name].

Technology Transfer Agreement ☐ No ☐ Yes MTA with LSU for plasma	samples. Expires Γ	December 12, 2022.	
Samples are being stored samples acquired for measurement assays have been obtained.		Yes (temporarily, page 1.25) ACTH will be destroyed once	L
Flesch-Kincaid reading level of con- (exclude boilerplate in assessing rea			

Medical Coverage Level:

Level 5 - The MAI (or designated clinician) is available by beeper or phone.

**

- **Level 1** The MAI administers all drugs and remains physically present in the experimental room during all or part of study session as determined by the Clinical Director.
- **Level 2** The MAI must be physically present in the experimental room during all or part of study session as determined by the Clinical Director.
- Level 3 The MAI must be present within the study building.
- Level 4 The MAI must be on the study campus.
- Level 5 The MAI is available by beeper or phone.

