(11) Are non-English speaking. *Justification:* There is no direct benefit to participants in this study. To include non-English speakers, we would have to translate the consent and other study documents and hire and train bilingual staff, which would require resources that we do not have and could not justify given the small sample size for each experiment. Additionally, the data integrity of some of the cognitive tasks and standardized questionnaires used in this study would be compromised as they have only been validated in English. Most importantly, ongoing communication regarding safety procedures is necessary when participants are undergoing MRI and tDCS procedures. The inability to effectively communicate MRI and tDCS safety procedures in a language other than English could compromise the safety of non-English speaking participants. *Assessment tool(s):* self-report.

The following exclusion criteria are new for the tDCS study:

(12) Participated in any brain stimulation session less than two weeks ago, or underwent brain stimulation exposure for treatment purposes in the last 6 months, including tDCS or transcranial magnetic stimulation (TMS). *Justification:* Prior exposure to brain stimulation may result in carry-over effects that could confound the results of this study. Participants may enroll in the study once the listed time periods have passed. *Assessment tool(s):* Participant medical history and physical (H&P).

Principal Investigator: [name].

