19) **Drug Use Survey (DUS):** An interviewer-administered questionnaire designed to collect information regarding lifetime history of substance use. To be completed once (Trait). Completion time: < 40 minutes.

Other Questionnaires

20) **Menstrual Cycle History Questionnaire:** To be administered at the start of each visit. Menstrual cycle information can be used to better understand gender differences should they be apparent in this study. To be completed each imaging visit (State). Completion time ~2 min.

Date: March 2, 2022 Principal Investigator: [name].

24.7 tDCS Behavioral Pilot

Up to the first **25 non-smoking participants** will participate in the tDCS Behavioral Pilot. This pilot study will examine the effect of tDCS stimulation on behavioral outcomes on the Parametric Flanker, N-back, and Amygdala Reactivity tasks in the *mock scanner*. **All procedures will be done as currently approved in the main tDCS study, except without MRI** (i.e. in the mock scanner only) **or characterization questionnaires** (only the tDCS Blinding Questionnaire will be administered to this group).

The tDCS Pilot will consist of an Orientation Session (consent, nurse visit, and task training, questionnaires and tDCS toleration test; approximately 3.5 hours), and three Mock Scanner/tDCS sessions (same as below, *24.6:Arm Design and Procedures;* approximately 5 - 6 hours for three 1-hour mock scanner sessions separated by two 1-hour breaks). The orientation and each of the 3 mock scanner/tDCS sessions can be completed on the same or separate days, as NRB resources and participant scheduling allow.

Because the Pilot will not include real MRI, the mock/scanner tDCS session will not include time for resting scans or structural image scans. The order of tasks will be re-arranged to reflect this difference. Order of tasks does not affect participant safety or study design. tDCS stimulation parameters will be the same as currently approved in the main tDCS protocol.

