tDCS power. Based on laboratory experience and literature review, the effect size for tDCS is the smallest of the study manipulations. Therefore, sample sizes falling in the appropriate power range for tDCS will also fall within the appropriate range for other manipulations in this study. In a meta-analytic review of the effect of tDCS on behavioral performance in cognitive tasks, it was found that effect size (Cohen's d) for anodal stimulation was about 0.49 (CI: 0.26, 0.72) for tDCS vs sham stimulation (Jacobson, Koslowsky, & Lavidor, 2011). Cathodal tDCS has been found to produce less reliable effect sizes than anodal tDCS. There is no independent cathodal tDCS condition in this study, and we have calculated power for anodal tDCS stimulation. The direction of tDCS effect is not classically known across each of the task paradigms, thus a two-tailed dependent samples t-test will be used. Approximately 34 participants in each group (smoker and non-smoker) will be required to achieve a power of 0.8 when assessing the effect of anodal tDCS vs sham (α-level of 0.05, two-tailed, matched pairs t-test, assuming a medium effect size for anodal tDCS stimulation).

Accounting for non-completion and non-compliance, we are requesting a maximum accrual of $\underline{60}$ smokers (enrollees) and $\underline{55}$ non-smokers (enrollees), with expectation of $\underline{35}$ completers in the smoker group, and $\underline{45}$ completers in the nonsmoker group.

Date: March 2, 2022

Principal Investigator: [name].

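### The 45 expected non-smoker completers in the tDCS arm include the no-MRI pilot, so a full pilot leaves about 25 for imaging against the 34 that Section 24.12 requires

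*Combined protocol and SAP*

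**What the plan says.** The sample-size statement for the arm is in Section 24.12: "Approximately 34 participants in each group (smoker and non-smoker) will be required to achieve a power of 0.8", for anodal tDCS against sham, with a two-tailed matched-pairs t-test at 0.05 and a medium effect. The effect size, d about 0.49 (CI 0.26 to 0.72), is introduced with "In a meta-analytic review of the effect of tDCS on behavioral performance in cognitive tasks". The section then requests 60 smokers and 55 non-smokers, expecting 35 and 45 completers.

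Section 24.4 qualifies the 45: "with the expectation of 45 completers (of either the Behavioral Pilot or tDCS Imaging study". The accrual summary at the front of the protocol says of the 55 non-smokers: "Up to the first 25 of these enrollees will complete the tDCS without MRI (Behavioral Pilot".

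Section 24.7 describes the pilot as run in the mock scanner only, and says that "the mock/scanner tDCS session will not include time for resting scans or structural image scans". Its purpose is behavioral: "This pilot study will examine the effect of tDCS stimulation on behavioral outcomes on the Parametric Flanker, N-back, and Amygdala Reactivity tasks".

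The first primary outcome in the Précis is change in BOLD signal and functional connectivity by drug or tDCS condition. Section 24.12 calls fMRI the main outcome measurement. Hypothesis 1.1.1 in Section 24.3 reads "Anodal-dlPFC tDCS will strengthen the within-network connectivity of the Executive Control Network compared to sham as measured by" resting-state functional connectivity, with healthy controls as one of the ordered groups.

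**The concern.** Placed beside a requirement of 34, an expectation of 45 reads as a margin of 11. But the 45 mixes two kinds of completer, and only one of them has imaging data. The documents as supplied give no separate target for non-smoker imaging completers; the enrollment table in Section 24.13 gives only 80 completers for the whole arm.

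Pilot participants contribute neither task BOLD nor resting connectivity, so they cannot count toward the 34 for those outcomes. Someone relying on Section 24.12 would take the non-smoker tDCS effect on connectivity to be tested with at least 0.80 power. With a full pilot it would not be, and a null result in the controls could be over-read.

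**Working it through.** **Inputs.**
- Section 24.12: two-sided 0.05, paired t-test, medium effect (taken as d = 0.5; cited d = 0.49, CI 0.26 to 0.72), about 34 per group, power 0.80.
- Sections 24.4 and 24.12: 55 non-smokers enrolled, 45 completers.
- Accrual summary and Section 24.7: up to the first 25 in the pilot, no MRI.
- Assumption: the overall completion rate, 45/55 = 0.82, applies equally to pilot and imaging enrollees. The documents give no separate rates.

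**Formula.** Power of the paired t-test from the noncentral t distribution, with n − 1 degrees of freedom and noncentrality d × √n.

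**Reproducing the plan's figure.** At d = 0.5 the smallest n with power of at least 0.80 is 34 (power 0.81). At d = 0.49 it is 35. The stated 34 is therefore correct for d = 0.5.

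**Imaging completers with a full pilot and no later scanning.**
- Enrollees left for imaging: 55 − 25 = 30.
- At the planned rate: 30 × 45/55 = 24.5, about 25.
- Upper limit (no imaging dropout): 30.
- Low case (all 25 pilot participants complete and the total is 45): 45 − 25 = 20.

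**Power for tDCS against sham in non-smokers, d = 0.5.**

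| n | Power |
|---|---|
| 20 | 0.56 |
| 25 | 0.67 |
| 30 | 0.75 |
| 34 | 0.81 |
| 45 | 0.91 |

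At n = 25, d = 0.49 gives 0.65. The limits of the cited interval give 0.24 (d = 0.26) and 0.93 (d = 0.72). The effect detectable with 0.80 power is 0.58 at n = 25, against 0.50 at n = 34.

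**How large the pilot can be.** With p pilot enrollees, expected imaging completers are (55 − p) × 45/55:
- p = 13: 34.4
- p = 14: 33.5
- p = 20: 28.6
- p = 25: 24.5

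So 34 is expected only with about 13 or fewer in the pilot. This limit depends on the completion rate. If every pilot participant completes and the total is 45, 45 − p ≥ 34 gives p ≤ 11. With no imaging dropout, 55 − p ≥ 34 gives p ≤ 21.

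**How much later scanning would close the gap.** With p = 25 and x pilot participants later scanned, (30 + x) × 45/55 is 33.5 at x = 11 and 34.4 at x = 12. About 12 would have to be scanned.

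**Contrasts little affected.** Smokers have no pilot; their 35 completers give 0.82 at d = 0.5. The smoker against non-smoker contrast is not powered in Section 24.12. At an assumed d = 0.5, two-sample t-test, it moves only from 0.53 (35 against 34) to 0.47 (35 against 25).

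**The case against.** The strongest reply is that the 34 is a behavioral calculation. Its effect size comes from cognitive task performance, the pilot measures performance on the arm's own tasks under the same stimulation, and behavioral performance is itself a listed primary outcome. Pooled, 45 non-smokers give 0.91. The 0.67 applies a behavioral d to imaging outcomes for which the documents give no tDCS effect size. This stands as a limit on scope. But no pooling is stated, Section 24.12 does not confine the 34 to behavior, and it offers no other tDCS-against-sham calculation for what it calls the main outcome.

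A second reply is that the general fMRI paragraph asks for about 21 participants, which 25 meets. That is true, but the figure is for a 0.5% signal change in a cognitive task, not tDCS against sham. Section 24.12 calls the tDCS effect the smallest of the manipulations and sizes the groups on it.

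Third, 25 is a ceiling, and pilot participants might be scanned later. Exclusion 12 in Section 24.5 bars only recent brain stimulation: "Participants may enroll in the study once the listed time periods have passed". The pilot eligibility checklist also requires suitability for MRI, so pilot completers would already be screened for it. Later scanning is thus possible, but the documents as supplied do not provide for it. The fact sheets were not available for review, and one of them covers the pilot.

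Finally, no sum in the plan is wrong. The fault is that a combined count stands beside a requirement that, for imaging, only part of it can meet.

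**Conclusion.** The point holds. If the pilot takes its full 25 and those participants are not scanned later, the non-smoker tDCS-against-sham contrast on imaging outcomes has about 25 completers and power of about 0.67 at d = 0.5, not 0.80. The value of 25 rests on equal completion in the two parts. The conclusion does not: at the most favorable completion the number is 30 and power is 0.75, still below both 34 and 0.80.

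The shortfall disappears if the pilot stays at about 13 or fewer, or if about 12 pilot participants are later scanned. It does not apply to smokers, nor to behavioral outcomes if pilot and imaging data are pooled.

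**What to change.** 1. In Sections 24.4 and 24.12, give expected non-smoker completers separately for the pilot and the imaging study, and say whether a pilot participant may later enter the imaging study.
2. In Section 24.12, restate the non-smoker imaging number and its power: about 25 and 0.67 with a full pilot, and 0.75 at most. Alternatively, if pilot places remain, limit the pilot to about 13 enrollees, so that about 34 imaging completers are expected at the 45/55 rate, and state that rate as the assumption (the limit is 11 to 21 under the other two completion scenarios).
3. State whether pilot and imaging behavioral data will be pooled, and that after a full pilot the 0.80 for non-smokers applies to behavioral outcomes only, and only if they are.

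No participants are added. The cost is protocol wording, plus either a smaller pilot or a lower stated power for one imaging contrast.
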